## Intercurrent events (ICE) and strategy

- (1) ICE1: Rescue treatment: efficacy data collected after rescue treatment will not be used (Hypothetical Strategy)
- (2) ICE2: Premature treatment discontinuation: efficacy data collected after treatment discontinuation will be included in the analysis regardless of attribution to treatment (Treatment Policy Strategy)

If both ICE1 and ICE2 occur for the same subject, addressing ICE1 takes precedence over ICE2. For example, if a subject took rescue medication at Week 10, and subsequently dropped out at Week 12 with no score at Week 24, then the method addressing ICE1 will be used.

3.4.2.1.2 Statistical Analysis for CFBL in SNOT-22 Total and Subdomain Scores 3.4.2.1.2.1 Part 1

Descriptive summary statistics on the values and changes from baseline will be presented for the SNOT-22 total and subdomain score at each analysis visit by treatment group.

3.4.2.1.2.2 Part 2

Statistical analysis of the CFBL in SNOT-22 total and subdomain scores at Weeks 2, 4, 6, 8, 12, 16, 20, 24, and 28/Follow-up will be carried out based on the Efficacy Analysis Set.

MMRM model without imputation: analysis will be carried out using MMRM model with the CFBL in SNOT-22 score as the dependent variable, and include the fixed, categorical effects of treatment, visit, treatment-by-visit interaction, and nasal polyp stratum as well as the continuous, fixed covariates of baseline score and baseline scoreby-visit interaction. An unstructured covariance structure shared across treatment groups will be used to model the within-subject errors. The covariance parameters in the above model will be fitted through a working model that assumes joint multivariate normality (MVN) of responses by maximizing the restricted likelihood (REML) under the working model, and the mean parameters will be estimated by generalized least squares after plugging in REML estimate of covariance parameters. In case the model does not converge with the unstructured covariance structure, the heterogenous Toeplitz structure (TOEPH) will be used instead. In case the model will not converge with the TOEPH structure, heterogenous compound symmetry (CSH) will be used instead. The Kenward-Roger approximation will be used to estimate denominator degrees of freedom and adjust nominal standard errors based on the inverse observed information from the working MVN model. Missing data will be handled by the MMRM under the missing at random (MAR) assumption.

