Least-squares means (LS-means) for change from baseline at each analysis visit will be provided for each treatment group and the difference between LYR-220 and sham treatment at each analysis visit will be estimated from the MMRM model.

Descriptive summary statistics on the values and changes from baseline will be presented for the SNOT-22 total and subdomain score at each analysis visit by treatment group.

Graphic displays of the results will be presented. The by-visit means and the standard errors for each treatment will be plotted against the analysis visit. In addition, the by-visit least squares mean changes and the standard errors for each treatment will also be plotted against the analysis visit.

- MMRM model with subject's worst score imputation: analysis will be carried out in the same manner as MMRM model without imputation except that post-rescue assessments will be imputed with subject's worst score from baseline (including baseline) through Week 28/Follow Up. Other missing data will be handled by MMRM model.
- Analysis of covariance (ANCOVA) with multiple imputation: an ANCOVA model will be performed to compare mean change from baseline in the SNOT-22 total and subdomain scores at Week 24 and Week 28/Follow-up between the LYR-220 and the sham treatment. Post-rescue Week 24 and Week 28/Follow-up assessments will be imputed with subject's worst score from baseline (including baseline) through Week 28/Follow Up. The ANCOVA model will include treatment, nasal polyp stratum as fixed-effect terms and baseline score as a covariate. The least-squares (LS) mean change for each treatment group, the LS mean difference between treatment groups will be reported. Missing data will be imputed with a multiple imputation procedure under the assumption of MAR. The imputation model will include nasal polyp stratum, baseline score and post baseline scores to impute the missing SNOT-22 score with monotone regression method and MCMC method will be used to produce monotone missing pattern. In case the imputation model does not converge, the model will be reduced to include nasal polyp stratum, baseline score, partial or no post baseline scores. There will be 50 imputed datasets derived using SAS PROC MI based on the pre-specified model above with a given random seed (protocol date). The ANCOVA model will be performed on each dataset after imputing the missing scores and PROC MIANALYZE will be used to combine the results.

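### The multiple-imputation model and its fallback omit treatment, so under the SAP's own MAR assumption one supporting ANCOVA understates a sustained or growing Week 24 effect (minor)

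*SAP*

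**What the plan says.** SAP Section 3.4.2.1.2.2 lists four Part 2 analyses of change in SNOT-22: MMRM without imputation, MMRM with post-rescue values set to the subject's worst score, ANCOVA with multiple imputation, and ANCOVA with LOCF. Section 3.4.2.2.2 applies the same methods to the cardinal symptom and loss-of-smell scores. Section 3.4.2.3.2 (CRS-PRO) and Section 3.4.2.4.2 (PGIS) say that missing data are not imputed.

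For the multiple-imputation ANCOVA the SAP says:

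- Assumption: "Missing data will be imputed with a multiple imputation procedure under the assumption of MAR".
- Imputation model: "The imputation model will include nasal polyp stratum, baseline score and post baseline scores to impute the missing SNOT-22 score with monotone regression method".
- Non-monotone gaps: "MCMC method will be used to produce monotone missing pattern".
- Fallback on non-convergence: "the model will be reduced to include nasal polyp stratum, baseline score, partial or no post baseline scores".
- Analysis model: "The ANCOVA model will include treatment, nasal polyp stratum as fixed-effect terms and baseline score as a covariate".

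The 50 imputed datasets come from PROC MI run on that pre-specified model. Post-rescue values are set to the subject's worst score first, so the imputation model acts only on other missing scores.

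The MMRM without imputation is specified to "include the fixed, categorical effects of treatment, visit, treatment-by-visit interaction, and nasal polyp stratum", and "Missing data will be handled by the MMRM under the missing at random (MAR) assumption". The worst-score MMRM is the same model apart from its post-rescue values.

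**The concern.** An imputation model should contain every term whose effect the analysis model estimates. Here treatment is that term, and it is absent. Under MAR with treatment in the model, a subject with a missing Week 24 score is assumed to follow observed subjects in the same arm with the same history. With treatment left out, that subject is assumed to follow a mixture of both arms, and arm enters only through whatever difference is already visible in the subject's own scores. If the fallback drops all post-baseline scores, the imputed values carry no information about arm.

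What is at stake is the size of the Week 24 difference in this one analysis, and its coherence with the worst-score MMRM. That MMRM treats rescue in the same way and declares the same assumption, but it conditions on treatment and treatment-by-visit. The two would disagree for a reason unrelated to the data. Missing scores need not come only from dropout: under Section 3.1.4.5 one unanswered item voids the SNOT-22 total.

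**Working it through.** The plan has no figure of its own to reproduce. Section 2.2.5 says that the sample size is not based on power, and the documents give no effect size, SD, correlation, effect shape or missing rate. All of these are assumptions below.

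**Inputs.** From the SAP: 1:1 allocation, about 20 per arm, visits at Weeks 0, 2, 4, 6, 8, 12, 16, 20 and 24, and the listed imputation terms. Assumed: a Week 24 effect of 1.0 SD; correlation a + (1 - a)exp(-lag/tau), lag in weeks, with (a, tau) = (0.3, 16) base, (0.2, 8) weak, (0.5, 24) strong; monotone dropout with the first missed visit uniform over Weeks 4 to 24; missing share m = 20%.

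**Formula.** Let δ be the vector of treatment effects by visit (zero at baseline) and Σ the within-arm covariance. Pooled over 1:1 arms without treatment, the covariance is Σ + 0.25δδ'. The imputation regression of Week 24 on the observed visits o has coefficients

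b = (Σ_oo + 0.25δ_oδ_o')⁻¹(Σ_o,24 + 0.25δ_oδ_24).

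The imputed values carry an arm difference of b'δ_o, a share s = b'δ_o/δ_24 of the true one. The estimate as a share of the true effect is

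R = (1 - m) + m·s̄, with s̄ the mean of s over dropout times.

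With treatment as a predictor, s = 1 and R = 1.

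**Numbers, base correlation.**

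- Sustained: s runs from 0.756 (Week 4 first missed) to 0.941 (Week 24 first missed), mean 0.829. R = 0.80 + 0.20 × 0.829 = 0.966.
- Linear rise from zero at baseline to full at Week 24: s̄ = 0.301. R = 0.80 + 0.20 × 0.301 = 0.860.
- Fallback with no post-baseline scores: s = 0. R = 0.80.

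| Effect shape | R base | R weak | R strong | Shrinkage |
|---|---|---|---|---|
| Sustained | 0.966 | 0.931 | 0.986 | 1-7% |
| 0.75 at Week 2, rising to full at Week 24 | 0.945 | 0.908 | 0.971 | 3-9% |
| 0.5 at Week 2, rising to full at Week 24 | 0.916 | 0.882 | 0.944 | 6-12% |
| Zero at baseline, full by Week 8, then flat | 0.918 | 0.886 | 0.943 | 6-11% |
| Zero at baseline, linear to full at Week 24 | 0.860 | 0.843 | 0.874 | 13-16% |
| Waning, 1.5 SD at Week 2 to 1.0 at Week 24 | 0.988 | 0.962 | 0.998 | 0-4% |
| Fallback, no post-baseline scores | 0.80 | 0.80 | 0.80 | 20% |

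Shrinkage is proportional to m, so it halves at 10% missing and is half as large again at 30%. Large simulations with Bayesian monotone-regression imputation agree with the sustained, steep-linear and waning rows to within 0.001; with treatment added they return the complete-data estimate.

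**Sensitivity.**

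- Non-monotone gaps (early stoppers with a follow-up score, so the MCMC step is used): 0-9% sustained and 2-17% for the steep linear rise.
- A different assumed grid (compound-symmetry and autoregressive correlations, rising or falling SDs): 0-9% sustained. There, an effect twice as large at Weeks 2-8 as later showed almost no shrinkage, and 1-3% inflation under compound symmetry of 0.6.
- Unbalanced gaps in the no-post-baseline fallback, 40% missing on active and 0% on sham: imputed active values carry 0.6/1.6 = 0.375 of the effect, so R = 0.6 + 0.4 × 0.375 = 0.75. The fallback loss equals the missing fraction only when missingness is balanced.

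**Trial size.** With 20 per arm, 0.8 SD, 20% missing and a one-sided 5% test (the level that the SAP's two-sided 90% intervals imply), rejection without against with treatment is 79% against 80% for a sustained effect (bias about 0.1 SE), 71% against 80% for the steep growing profile (about 0.3 SE), and 3.7% against 5.8% with no effect (Monte Carlo SE about 1 point).

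**The case against.** The strongest objection concerns the estimand. Section 3.4.2.1.1 handles premature discontinuation by treatment policy, and stopping early here means losing or removing the matrix, so some loss of effect is plausible. With 20% missing and early stoppers losing 25%, 50% or 100% of the effect, the truth is 1 - 0.2 × loss = 0.95, 0.90 or 0.80. The listed model gives 0.93-0.99 (sustained) and 0.85-0.88 (steep growing); the model with treatment gives 1.00 throughout. The listed model is closer in five of the six combinations; the exception is a growing effect with 25% loss. This stands as a limit: adding treatment restores MAR given arm and does nothing about loss of effect off drug, a weakness that the MMRM shares. It is not a defence of the listed model, because that shrinkage depends on correlation and effect shape and is not a stated model of off-drug behaviour. The SAP declares MAR.

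Three further objections stand in part. First, the largest figures need special conditions: 13-16% needs an effect that starts at zero and reaches full size only at Week 24, and the full missing-fraction loss needs non-convergence followed by reduction to no post-baseline scores, where the text also allows some to be kept. Second, a gap between this ANCOVA and the MMRM without imputation could not be put down to this omission alone, because that MMRM discards post-rescue data; the worst-score MMRM is the fair comparator. Third, the SAS Procedures appendix listed in the SAP contents was not in the text reviewed, and Section 6 places programming specifications in a separate document, so the code may already name treatment.

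**Conclusion.** The imputation model is wrong as written, and the point is minor. Under the declared MAR assumption, omitting treatment shrinks a sustained or growing Week 24 effect in the multiple-imputation ANCOVA, for SNOT-22 and for the cardinal symptom and loss-of-smell scores. At an assumed 20% missing with monotone dropout, the size is about 1-7% (sustained), 3-16% (growing, by shape), 0-4% (waning), or the whole missing fraction in the extreme fallback. No size is claimed for Week 28. With no effect or nothing missing there is no bias.

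A reader might infer more in three ways, none of which the documents support:

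- That the trial's efficacy result as a whole is biased towards no effect. Both MMRMs and the LOCF ANCOVA do not use this model, post-rescue values bypass it, and Section 3.4.1 makes efficacy secondary.
- That 13-16% is the general figure for a growing effect. It belongs to one steep shape; milder growth gives 3-12%.
- That the listed analysis is always conservative. If early stoppers lose much of the effect, it can overstate the treatment-policy effect.

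Confidence is moderate, because the finding rests on the SAP's body text and every size rests on assumed inputs.

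**What to change.** Before the primary lock, add randomised treatment as a predictor in the MCMC step and in the monotone regression, and keep it in every reduced fallback model. State that the analysis is then MAR given arm, in line with the worst-score MMRM, and that it does not address loss of effect after early stopping, where the estimate can overstate the treatment-policy effect as the MMRM can.

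Use one pooled model and do not impute by arm. At 20% missing, a by-arm Week 24 regression fits 10 parameters (intercept, polyp stratum, baseline, seven earlier visits) to about 16 subjects: 16 - 10 = 6 residual degrees of freedom. The pooled model with treatment fits 11 to about 32: 32 - 11 = 21.

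The cost is one extra parameter and a few words in the SAP. In the 20-per-arm simulation (sustained effect) the mean pooled standard error was 0.322 with treatment and 0.323 without.

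If the SAS appendix or the programming specifications already include treatment, correct the SAP text to match. If the lock has passed, Section 4.2 makes the change post hoc; report the corrected analysis as such beside the listed one.

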3.4.2.8 CFBL in Nasal Inflammatory Biomarker Level at Week 25/Follow-up

Data will not be available by the time of final analysis. Hence, data will not be summarized and analyzed.

3.4.2.9 PGIC at Week 24

3.4.2.9.1 Part 1

Descriptive summary statistics on the values will be presented.

3.4.2.9.2 Part 2

The endpoint will be summarized using the number and percentage of subjects in each category by treatment group. Comparison between LYR-220 group and the sham procedure group in having "very much better" or "much better" impression will be performed using a Cochran-Mantel-Haenszel (CMH) test controlling for nasal polyp status. The general association p-value will be provided. The odds ratio and the corresponding CI will also be provided. The point estimates and CI for the treatment group differences in proportions will be calculated using Agresti's (2013, page 231) approximation to the Miettinen and Nurminen (1985) method by using pseudo-standard errors.

3.4.2.10 Conversion to a Candidate No Longer Requiring Revisions Surgery 3.4.2.10.1 Part 1

This responder endpoint will be summarized using the number and percentage of subjects that meet the criteria for no longer requiring revision surgery in each treatment group.

#### 3.4.2.10.2 Part 2

This responder endpoint will be summarized using the number and percentage of subjects that meet the criterion for no longer requiring revision surgery in each treatment group. Comparison between each LYR-220 group and the sham procedure group will be performed using the CMH test controlling for nasal polyp status. The general association p-value will be provided. The odds ratio and the corresponding CI will also be provided. The point estimates and CI for the treatment group differences in proportions will be calculated using Agresti's (2013, page 231) approximation to the Miettinen and Nurminen (1985) method by using pseudo-standard errors.

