To evaluate the effect of LYR-220 in reducing nasal inflammatory marker levels at Week 25	- CFBL in nasal inflammatory marker levels at Week 25

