9.8.1.5 Conversion to A Candidate No Longer Requiring Revisions Surgery

This responder endpoint will be summarized using the percentage of subjects that meet the criteria for no longer requiring revision surgery in each treatment group. Comparison between each LYR-220 group and the sham procedure group will be performed using the CMH test controlling for nasal polyp status.

9.8.1.6 CFBL in Nasal Inflammatory Marker Levels at Week 25

Mean CFBL in nasal inflammatory marker levels at Week 25 will be compared between each LYR-220 group and the sham procedure group using an ANCOVA model with fixed-effect terms for treatment group and nasal polyp status with baseline score as a covariate.

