# 2.1.2 Secondary Objectives

The secondary objectives are to:

- 1. Evaluate the safety and tolerability of LYR-220.
- 2. Evaluate the efficacy of LYR-220 in improving total 22-item Sino-Nasal Outcome Test (SNOT-22) and subdomain scores through Week 28/Follow Up.
- 3. Evaluate the efficacy of LYR-220 in improving 3 cardinal symptoms (3CS) and individual cardinal symptom score through Week 28/Follow Up.
- 4. Evaluate the efficacy of LYR-220 in improving loss of smell symptom score through Week 28/Follow Up for subjects with moderate-to-severe score at baseline.
- Evaluate the efficacy of LYR-220 in improving total Patient-Reported Outcome Measure for Chronic Rhinosinusitis (CRS-PRO) and subdomain scores through Week 28/Follow Up.
- 6. Evaluate the time to first rescue treatment recommendation through Week 28/Follow Up.
- 7. Evaluate the percentage of subjects who have uncontrolled CRS symptoms requiring systemic/oral corticosteroids or sinonasal surgery through Week 28/Follow Up.
- 8. Evaluate the effect of LYR-220 in reducing ethmoid cavity opacification as per computed tomography (CT).
- 9. Evaluate the efficacy of LYR-220 in improving subject perception of symptom severity and improvement.
- Evaluate the effect of LYR-220 in converting a subject to not requiring revision surgery.
- 11. Evaluate the effect of LYR-220 in reducing nasal inflammatory marker levels at Week 25/Follow Up.

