## 2.3.3 Secondary Efficacy Endpoints

The secondary efficacy endpoints are:

- 1. Change from baseline (CFBL) in SNOT-22 total and subdomain scores at Weeks 2, 4, 6, 8, 12, 16, 20, 24, and 28/Follow Up.
- 2. CFBL in the 7-day average composite score of 3CS and individual cardinal symptom scores at Weeks 2, 4, 6, 8, 12, 16, 20, 24, and 28/Follow Up.
- 3. CFBL in the 7-day average score of loss of smell for subjects with baseline score ≥2 at Weeks 2, 4, 6, 8, 12, 16, 20, 24, and 28/Follow Up.
- 4. CFBL in CRS-PRO total and subdomain scores at Weeks 2, 3, 4, 6, 8, 12, 16, 20, 24, and 28/Follow Up.
- 5. Time to first rescue treatment recommendation through Week 28/Follow Up.
- 6. Systemic/oral corticosteroid use or sinonasal surgery recommendation through Week 28/Follow Up.
- CFBL in bilateral percent ethmoid cavity opacification by CT at Week 25/Follow Up.
- 8. CFBL in PGIS score at Weeks 8, 16, and 24.
- 9. PGIC score at Week 24.
- 10. No longer a candidate for revision surgery.
- 11. CFBL in nasal inflammatory marker levels at Week 25/Follow Up.

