3.1.10.2 Algorithm for Treatment Emergent Adverse Events (TEAE)

TEAE is defined in Section 3.6.1.

For deriving the TEAE flag, the following process of temporary date imputation is done for adverse event (AE) start date. The date imputation algorithm for incomplete adverse event start dates is described in the following table. Classification of adverse event (TEAE or not) is then done using the imputed date.

In the following table, all dates are presented using an YYYY-MM-DD format. As an example, suppose the investigational medicinal product (IMP) administration = 2022-08-11 and several AEs have incomplete start dates.

Table 6. Imputation Rules for Missing AE start Date

Description of incomplete date   Imputed nume		Example	
	date	Character date	Imputed date
Day is missing			
YYYY-MM < YYYY-MM of [IMP	YYYY-MM-01	2022-07-XX	2022-07-01
admin.]			

YYYY-MM = YYYY-MM of [IMP	Min ([IMP admin.],	2022-08-XX	Min (2022-08-
admin.]	AE end date)		11, AE end date)
YYYY-MM > YYYY-MM of [IMP	YYYY-MM-01	2022-09-XX	2022-09-01
admin.]			
Day and month are missing			
YYYY < YYYY OF [IMP admin.]	YYYY-01-01	2021-XX-XX	2021-01-01
YYYY = YYYY OF [IMP admin.]	Min ([IMP admin.],	2022-XX-XX	Min (2022-08-
	AE end date)		11, AE end date)
YYYY > YYYY OF [IMP admin.]	YYYY-01-01	2023-XX-XX	2023-01-01
Day, month, and year are missing			
XXXX-XX-XX	Min ([IMP admin.],		Min (2022-08-
	AE end date)		11, AE end date)

YYYY = non-missing year, MM = non-missing month, DD = non-missing day, XX = missing field.

Actual data values as they appear in the original eCRFs will be presented in the data listings.

3.1.10.3 Handling of Missing Data and Data Post-Rescue Treatment for Efficacy Endpoints 3.1.10.3.1 Part 1

No imputation will be performed. All efficacy data will be summarized descriptively.

#### 3.1.10.3.2 Part 2

The details for handling missing data and intercurrent events for the secondary efficacy endpoints are specified in the estimand framework in Section 3.4.2. There will be no imputation for missing bilateral percent ethmoid cavity opacification by CT or nasal inflammatory biomarker assessments.

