#### 4.2 Primary Lock Analysis

A Primary Lock Analysis (PA) will be conducted to support a late-breaking presentation of high-level results from this BEACON study at the annual meeting of the American Rhinologic Society (ARS) in September 2023. The SAP will be finalized and signed prior to this analysis. Any changes to the pre-planned analyses in this SAP that affects statistical analysis after the primary lock analysis will be considered posthoc. The study team members who are involved in data cleaning for the final data base lock will not receive the detailed patient-level results from the PA.

The PA will be performed after all subjects in Part 1 and Part 2 complete Week 24 visit. After the database is locked (i.e., freeze of eCRFs), the subject's treatment allocation will be unblinded.

The analysis data sets (i.e., SDTM and ADaM) for this analysis will be locked. Selected data will be generated as listed below.

- · Disposition,
- Demographics,
- Baseline disease characteristics,
- Change from baseline (CFBL) in SNOT-22 total score at Weeks 2, 4, 6, 8, 12, 16, 20, 24 and 28,
- CFBL in the average composite score over the preceding 7 days of 3 cardinal symptoms (3CS) and individual cardinal symptom scores at Weeks 2, 4, 6, 8, 12, 16, 20, 24 and 28,
- Overview of Adverse Events.
- Treatment-Emergent Adverse Events by Preferred Term,
- Treatment-Emergent Adverse Events by System Organ Class and Preferred Term,
- Product-Related Treatment-Emergent Adverse Events by System Organ Class and Preferred Term,
- Treatment-Emergent Serious Adverse Events by System Organ Class and Preferred Term.
- Product-Related Treatment-Emergent Serious Adverse Events by System Organ Class and Preferred Term,
- Treatment-Emergent Adverse Events Leading to Discontinuation of Study Treatment by System Organ Class and Preferred Term.

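### The SAP cancels all analysis of Week 25 nasal inflammatory markers, a listed secondary endpoint with a protocol ANCOVA, and commits to no later analysis

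*SAP*

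**What the plan says.** **Protocol.** Section 3 lists "CFBL in nasal inflammatory marker levels at Week 25" among the secondary efficacy endpoints, and 9.8.1 repeats it. Section 9.8.1.6 gives the analysis: "nasal inflammatory marker levels at Week 25 will be compared between each LYR-220 group and the sham procedure group using an ANCOVA model", with treatment group and nasal polyp status as fixed effects and the baseline value as covariate. Missing marker assessments are not to be imputed (9.8.1.1.1).

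**SAP, where the endpoint is kept.** Objective 11 in 2.1.2 reads "Evaluate the effect of LYR-220 in reducing nasal inflammatory marker levels at" Week 25. Endpoint 11 in 2.3.3 is "CFBL in nasal inflammatory marker levels at Week 25/Follow Up". Section 3.1.4.17 describes the swabs, and 3.1.10.3.2 carries a missing-data rule: "There will be no imputation for missing bilateral percent ethmoid cavity opacification by CT or nasal inflammatory biomarker assessments".

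**SAP, where the analysis is cancelled.** Section 3.4.2.8 consists of one statement: "Data will not be available by the time of final analysis. Hence, data will not be summarized and analyzed".

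**SAP, surrounding rules.** Section 5 declares that nothing differs from the analyses in the protocol. Section 4.2 says that any change to the SAP's planned analyses "that affects statistical analysis after the primary lock analysis will be considered posthoc". Section 4.3 has the CSR written from the final tables, figures and listings.

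**The concern.** Late assay results are a reason to analyse later. They are not in themselves a reason to plan no analysis. The SAP neither withdraws the endpoint nor says that the assays failed, yet it names no later analysis, addendum or timetable. A listed secondary objective therefore has no planned route to an answer.

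What is at stake is how the markers get reported if results arrive later. By then treatment allocation will have been unblinded and the main symptom results produced. Whether to report the markers, which ones, and by which assay would be decided with those results in view and with no binding plan in the SAP.

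**Working it through.** No power or alpha figure bears on this point, and SAP 2.2.5 says the sample size is not power-based. The check is a comparison of sections plus two counts.

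1. **Is the endpoint still live?** Yes. It stands in SAP 2.1.2 and 2.3.3, and the rule in 3.1.10.3.2 presupposes an analysis.

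2. **How many secondary efficacy endpoints lack an analysis?** SAP 2.3.3 lists 11. Sections 3.4.2.1 to 3.4.2.7, 3.4.2.9 and 3.4.2.10 give a summary or test for endpoints 1 to 10. Only endpoint 11 has none: 11 − 1 = 10 covered. Section 3.4.2.8 makes no split by study part, so even the descriptive Part 1 summary given for the other endpoints is absent.

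3. **Would waiting conflict with the protocol?** No. Protocol 9.8 places efficacy analyses after the last subject's Week 28 visit or earlier withdrawal. That sets an earliest time, not a deadline.

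4. **Can the three statements coexist?**
   - Protocol 9.8.1.6: "Mean CFBL in nasal inflammatory marker levels at Week 25 will be compared".
   - SAP 3.4.2.8: no summary and no analysis.
   - SAP Section 5: no departure from the protocol's analyses.

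   They cannot all hold. If 3.4.2.8 stands, Section 5 is wrong.

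5. **Does another rule record the omission or bring the analysis back?** None that could be read. SAP Section 1 has the CSR document changes from the final SAP. The final SAP plans no marker analysis, so omitting it is not such a change. The final outputs behind the CSR (4.3) will contain no marker results. Section 4.2 unblinds treatment at the primary lock and produces SNOT-22 total, 3CS and individual symptom results then. Adding a marker analysis afterwards would change what the signed SAP plans, so 4.2 could be read as making it post hoc.

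6. **How much choice would a later analyst have?** Protocol 8.4.3 and SAP 3.1.4.17 refer only to T2 inflammatory markers, with one protein and one RNA swab per side. They name no individual markers and give no transformation, detection-limit rule or method for combining sides. The efficacy visit windows (SAP Tables 1a to 1f) include none for the swabs. SAP 3.1.7 applies no multiplicity adjustment. The protocol's ANCOVA fixes the model terms but not the response variable.

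7. **Scale of collection.** 2 swabs per side × 2 sides × 2 visits (Day 1 and Week 25) = 8 per subject. With about 40 subjects in Part 2, 8 × 40 = 320. This is an approximate planned maximum that assumes complete collection; the documents give no dropout rate.

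8. **Effect on other analyses.** With no multiplicity adjustment, omitting this endpoint changes no significance level elsewhere. The primary endpoint is a safety endpoint and is untouched.

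**The case against.** The strongest reply is that the SAP hides nothing. It states the omission and gives a reason, and it is to be finalised before the primary lock and unblinding. Keeping the endpoint in the objectives and endpoint list fits deferral better than withdrawal. The ANCOVA is already in the protocol, so a later run that follows it could fairly be called protocol-specified but deferred. Protocol 4.2 gives the markers a developmental role, in refining endpoints for the wider programme.

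Most of this stands, and it rules out several stronger readings that a reader might infer:

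- *The omission was driven by results.* The documents give no sign of this. The reporting risk lies in a later analysis, not in the present statement.
- *The swabs go unused.* Section 3.4.2.8 speaks only of availability by the final analysis. It does not say that samples will not be assayed or never reported.
- *A later analysis necessarily loses its pre-specified status.* The model predates the lock, so 4.2 makes that status contestable and does not settle it.
- *The markers are the only direct measure of an effect on inflammation.* They are the only molecular measure planned, but CT opacification at Week 25, read by a core laboratory, keeps its ANCOVA (SAP 3.4.2.7).
- *The change is recorded nowhere.* The SAP contents list an Appendix E summarising changes from the protocol. Its content was not available for this review, so the change may be recorded there.

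The reply does not remove the absence of any commitment to analyse late data, or the conflict between Section 5 and 3.4.2.8. The protocol model alone also leaves the choices in step 6 open.

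**Conclusion.** The point holds as a gap in the plan and an internal contradiction. SAP 3.4.2.8 cancels the analysis of a retained secondary endpoint for timing alone and commits to nothing later, and Section 5 is incorrect as written whatever Appendix E contains. Any later analysis could be called post hoc under 4.2 and would be exposed to selection among markers and assays.

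It is a minor point: one of 11 secondary efficacy endpoints in a Phase II trial whose primary endpoint is safety. The conclusion assumes that assay results will eventually exist and that no separate document, including Appendix E, already commits to analysing them. If such a commitment exists, what remains is to correct Section 5 and cross-refer to it.

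**What to change.** 1. Replace SAP 3.4.2.8 with a commitment to run the ANCOVA of protocol 9.8.1.6 (treatment, nasal polyp status, baseline) on Part 2 when assay data are available, summarise Part 1 descriptively as for the other endpoints, and report the results in a CSR addendum whatever they show.
2. Before any assay result is seen, issue a dated SAP addendum that names the markers and states whether protein, mRNA or both are analysed. It should also set any transformation, the detection-limit rule, the combination of the two sides and the visit window. Rerunning the protocol model without these would leave the selection problem in place.
3. List the deferral in SAP Section 5, and make Appendix E agree with it.
4. If the sponsor means to abandon the endpoint, say so with a reason and remove it from SAP 2.1.2 and 2.3.3.

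The cost is a few paragraphs of SAP text and, for the deferred analysis, a short later addendum to the CSR. No additional data collection is needed.
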